9.1.9 Contraception and Pregnancy Avoidance Procedure

From date of signing of ICF, throughout the duration of the study, and for 30 days after last dose of study medication, females of childbearing potential* must use acceptable method(s) of contraception; nonsterilized** male subjects who are sexually active with a female partner of childbearing potential* must use acceptable method(s) of contraception throughout the duration of the study, and for 12 weeks after last dose of study medication. In addition, males must be advised not to donate sperm during this period.

*Females NOT of childbearing potential are defined as those who have been surgically sterilized (hysterectomy, bilateral oophorectomy or tubal ligation) or who are postmenopausal (e.g., defined as at least 2 years since last regular menses with an FSH>40 IU/L or at least 5 years since last regular menses, confirmed before any study medication is implemented).

**Sterilized males should be at least 90 days post vasectomy and confirm that they have obtained documentation of the absence of sperm in the ejaculate.

Acceptable methods of contraception in this study include:

- Abstinence, defined as refraining from heterosexual intercourse during the entire period of risk associated with the study treatments. If heterosexual intercourse does occur, an acceptable method of birth control is required.
- Surgical sterilization or postmenopausal
- Condom, diaphragm, or cervical cap with spermicide
- Hormonal contraception, including oral, injectable, transdermal, or implantable methods
- Intrauterine device (IUD)

Subjects will be provided with information on acceptable methods of contraception as part of the subject informed consent process and will be asked to sign an ICF stating that they understand the requirements for avoidance of pregnancy, and sperm donation during the course of the study.

Study No. CVN424-201 Page 38 of 73

Protocol v. 4.0 14 July 2021

9.1.10 Pregnancy

Women who are pregnant or breastfeeding will not be included in this study.

If any subject is found to be pregnant during the study, she should be withdrawn, and any sponsor-supplied drug should be immediately discontinued. In addition, any pregnancies in the partner of a male subject during the study or for 12 weeks after the last dose, should also be recorded following authorization from the subject's partner.

If the pregnancy occurs during administration of active study medication, e.g., after Visit 1 or within 30 days of the last dose of active study medication, the pregnancy should be reported immediately, using a pregnancy notification form, to the contact listed in Section 1.0.

Should the pregnancy occur during or after administration of blinded drug, the investigator must inform the subject of their right to receive treatment information. If the subject chooses to receive unblinded treatment information, the individual blind should be broken by the investigator. Subjects randomized to placebo need not be followed.

If the female subject and/or female partner of a male subject agrees to the primary care physician being informed, the investigator should notify the primary care physician that the subject/female partner of the subject was participating in a clinical study at the time she became pregnant and provide details of treatment the subject received (blinded or unblinded, as applicable).

All reported pregnancies will be followed up to final outcome, using the pregnancy form. The outcome, including any premature termination, must be reported to the sponsor. An evaluation after the birth of the child will also be conducted.

9.1.11 ECG Procedure

Standard 12-lead ECGs will be recorded at timepoints as specified in the Schedule of Study Procedures (Appendix A). Triplicate ECGs will be taken at each scheduled time. Additional unscheduled ECGs may be recorded where clinically necessary for subject safety.

When an ECG is scheduled at the same time as blood draws or vital signs then the blood draws and vital signs will take priority and the ECG will be obtained before or after the scheduled blood draw/vital sign assessment.

ECG recordings will be obtained in a supine position following an approximate 10-minute period of rest. Should technical difficulties occur during recording of the ECG, a reasonable attempt should be made to repeat the ECG shortly after the failed attempt.

ECGs will be interpreted by qualified personnel at the central ECG lab. The investigator or sub-investigator will categorize the ECG findings using 1 of the following categories: within normal limits, abnormal but not CS, or abnormal and CS. All 12-lead ECGs will be stored for manual measurement of intervals, if necessary. Twelve-lead ECGs will be recorded using an ECG machine that automatically calculates the heart rate and measures PR interval, RR interval, QRS interval, QT interval, and QTcF and QTcB (Fridericia's and Bazett's correction method) intervals.

Study No. CVN424-201 Page 39 of 73

Protocol v. 4.0 14 July 2021

9.1.12 Pharmacogenomic Sample Collection

Every subject must sign ICF/be consented for sampling of whole blood for pharmacogenomic analysis in order to participate in the study.

One whole blood sample for DNA isolation and genotyping will be collected at time points specified in the Schedule of Study Procedures (Appendix A) and stored under frozen conditions. In addition, whole blood samples will be collected at time points specified in the Schedule of Study Procedures (Appendix A) for ribonucleic acid (RNA) pharmacogenomic analysis.

Specific purposes of this pharmacogenomic study include:

- Identifying genetic reasons why certain people respond differently to CVN424
- Finding out more information about how CVN424 works
- Generating information needed for research, development, and regulatory approval of tests to predict response to CVN424
- Identifying variations in genes related to the biological target of CVN424

This information may be used, for example, to develop a better understanding of the safety and efficacy of CVN424 and other study medications, and for improving the efficiency, design and study methods of future research studies.

The samples will be stored for no longer than 15 years after completion of the CVN424 study and/or until the drug development of CVN424 is no longer actively pursued by the sponsor or its collaborators. No samples will be stored for longer than permitted by the applicable law and samples will be destroyed upon notification from the sponsor. "Stored samples" in this context are defined as samples that are double coded (the samples are stripped of all personal identifying information but a key links the samples to the clinical data collected from the sample donor) and are used in the analysis of investigational drug or related drug.

The sampling of whole blood for pharmacogenomic and genotyping analysis is mandatory; every subject must sign the ICF in order to participate in this study. Blood serum/plasma, DNA and/or RNA samples can be used to identify markers (e.g., potential metabolites, or drug metabolic enzyme and transporter polymorphisms) that may contribute to the variability in CVN424 PK, pharmacodynamics, or safety. Also, since pharmacogenomics is an evolving science, many genes and their functions are not yet fully understood. Future data may suggest a role of some of these genes in drug response, which may lead to additional hypothesis-generating exploratory research and diagnostic development on stored samples.

If necessary and feasible, a second aliquot of blood may be taken if isolation of DNA from the first sample was not successful or possible.

Detailed instructions for the handling and shipping of samples are provided in a separate lab manual.

Each pharmacogenomic sample for a study subject should be identifiable on the requisition form with the subject identification number.

Study No. CVN424-201 Page 40 of 73

Protocol v. 4.0 14 July 2021

9.1.13 PK Sample Collection

9.1.13.1 Collection of Blood for PK Sampling

Blood samples (one sample per scheduled time) for analysis of CVN424 plasma concentrations will be collected into chilled Vacutainers containing K₂EDTA according to the schedules in Table 5 and Appendix A.

Instructions for sample processing and shipment are provided in a separate lab manual.

Serial blood samples for determination of CVN424 concentrations in plasma will be collected according to Table 5.

 Table 5
 Collection of Blood Plasma Samples for PK Analysis

Study Day	Time Post-dose (hours).
1, 8	Pre-dose and at 3 h post-dose
15, 27	Post-dose (time not specified)
22	Pre-dose and at 1, 1.5, 2, 4, and 6 h post-dose
35	Washout (time not specified)

The PK samples will be collected at the nominal time point within the allowable windows per Table 8. The actual time of sample collection will be recorded on the source document and eCRF.

Placebo samples will not be analyzed by the bioanalytical laboratory except 2 samples per subject receiving placebo, 1 following first-dose (i.e., 3 h post-dose) and 1 at the Day 27 visit to ensure from a safety perspective that no additional subjects could have been on active treatment.

9.1.13.2 Bioanalytical Methods

Plasma concentrations of CVN424 will be measured by high-performance liquid chromatography with tandem mass spectrometry or an alternative method of comparable sensitivity and specificity.

Plasma samples will be archived to support potential post hoc laboratory testing (e.g., biomarkers, potential characterization of unknown CVN424 metabolites).

9.1.14 PK Parameters

PK parameters of CVN424 will be derived using non-compartmental analysis methods from the concentration-time data for all evaluable subjects. Actual sampling times, rather than scheduled sampling times, will be used in all computations involving sampling times. The following PK parameters (Table 6) will be determined from concentrations of CVN424 in plasma:

Study No. CVN424-201 Page 41 of 73

Protocol v. 4.0 14 July 2021

Table 6	Pharmacokin	etic Parameters
---------	-------------	-----------------

Symbol/Term	Definition
AUC_∞	Area under the plasma concentration-time curve from time 0 to infinity, calculated as $AUC_{\infty}=AUC_t+C_{last}/\lambda_z$, where C_{last} is the last quantifiable concentration.
AUC ₆	Area under the plasma concentration-time curve from time 0 to 24 hours, calculated using the linear trapezoidal rule.
C_{max}	Maximum observed concentration.
CL/F	Apparent clearance after extravascular administration, calculated as Dose/AUC $_{\infty}$ after a single dose.
λ_{z}	Terminal elimination rate constant, calculated as the negative of the slope of the log-linear regression of the natural logarithm concentration-time curve during the terminal phase.
$t_{1/2z}$	Terminal elimination half-life, calculated as $ln(2)/\lambda_z$.
t_{max}	Time to reach C_{max} .
V_z/F	Apparent volume of distribution during the terminal phase after extravascular administration, calculated as (CL/F)/ λ_z .

Additional plasma PK parameters may be calculated, including analyses by gender (if possible).

9.1.15 Documentation of Screen Failure

Investigators must account for all subjects who sign ICF. If the subject is found to be not eligible at this visit, the investigator should complete the eCRF screen failure form.

The primary reason for screen failure is recorded in the eCRF using the following categories:

- PTE/AE
- Did not meet inclusion criteria or did meet exclusion criteria
- Significant protocol deviation
- Lost to follow-up
- Voluntary withdrawal
- Study termination
- Other

Subject numbers assigned to subjects who fail screening should not be reused.

If a subject fails screening, but is later successfully re-screened, the data for the subject will be entered as if these were two separate subjects. Therefore, the data should be entered as follows:

- 1. The screen failure data should be entered as a screen failure subject.
- 2. Re-screened subjects should be assigned a new subject number and treated as a stand-alone subject.

Study No. CVN424-201 Page 42 of 73

Protocol v. 4.0 14 July 2021

9.1.16 Documentation of Randomization

Only subjects who meet all of the inclusion criteria and none of the exclusion criteria are eligible for randomization into the treatment phase.

If the subject is found to be not eligible for randomization, the investigator should record the primary reason for failure on the applicable eCRF.

9.2 Monitoring Subject Treatment Compliance

Study medication will first be administered (on Day 1) while subjects are under observation at the investigative site. Subsequent doses will be self-administered at home, or at the investigative site on selected Study Visit days. The date and time of each observed dose will be recorded in the source documents and on the eCRFs.

At each weekly visit, subjects will return to the site all study medication bottles, whether empty or full, for assessment of treatment compliance.

An inventory of the study medication supplies dispensed will be performed by the site pharmacist or authorized study designee and recorded onto the Drug Accountability Log in the subject's source document records or equivalent.

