6.0 STUDY DESIGN AND DESCRIPTION

6.1 Study Design

This is a phase 2, randomized, double-blind, placebo-controlled, multicenter study of two dose levels of oral CVN424 (low-dose 50 mg, high-dose 150 mg) in Parkinson's disease (PD) patients with motor fluctuations. The overall study design is depicted in Figure 1.

Figure 1. Schematic design of study

Approximately 135 subjects with Parkinson's disease will be enrolled. Following baseline safety and efficacy assessments, subjects will be randomized in a 1:1:1 ratio into one of 3 study arms to receive low-dose CVN424, high-dose CVN424 or matching placebo. The planned low-dose and high-dose levels will be 50 and 150 mg CVN424 per day, respectively, as shown in Table 3.

Subjects not randomized to placebo will initiate treatment with 50 mg CVN424 on Day 1. Thereafter, the low-dose arm will continue to receive 50 mg per day, while the high-dose cohort will increase their dosage to 150 mg CVN424 per day beginning on Day 8 ±2 days and continuing thereafter. This step-wise increase is intended to limit the changes that the first dose of CVN424 may elicit in vital signs (notably, increased temperature and heart rate, which were dose-dependent and not clinically significant in a healthy volunteer study). Investigator or their delegate will manage incident AEs according to their medical judgment.

Study drug supply will be dispensed (as suspension in amber colored bottles) on Day 1 and at subsequent weekly study visits. Study drug will be self-administered each morning on an outpatient basis as an oral suspension. Dosing on Day 1, Day 8 and Day 22 visits will be observed at the study site by Investigator or their delegate. For Visit Days 8 and 22, dosing of study drug (but not subjects' other medications) will be deferred until after collection of a blood sample for determination of the study drug "trough" concentration.

Study No. CVN424-201 Page 23 of 73

Protocol v. 4.0 14 July 2021

Following dosing on days 1 and 8, subjects will remain on site until at least 3 h after dosing for safety and PK assessments. Investigator or their delegate will manage any incident AEs.

The study visit schedule is summarized in Table 1. Follow-up assessments will occur approximately 7 days after the final (Day 27 or 28) dose. A summary of activities scheduled at each study visit is included in Section 9.3. A Schedule of Study Procedures is listed in Appendix A.

Table 1 Subject Visit Schedule

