9.3.1.7 Study Visit, Day 27 ± 1 day

All subjects will present to their local site on Day 27 ± 1 day, returning to the site all bottles of study medication, whether empty or unused.

An untimed blood sample for PK analysis will be collected.

All subjects will have completed a Patient Motor Diary recording their capabilities, limitations and motor symptoms over the prior 2 days (e.g., Days 25 and 26). Site will conduct assessments to

Study No. CVN424-201 Page 45 of 73

Protocol v. 4.0 14 July 2021

complete the UPDRS. PGI, CGI, Epworth Sleepiness Scale, and Questionnaire for Impulsive-Compulsive Disorders.

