12.1.3 PK Analysis

The concentration of CVN424 in plasma will be summarized by dose over each scheduled sampling time using descriptive statistics. Individual plasma concentration data versus time will be presented in a data listing.

PK parameters of CVN424 will be derived using non-compartmental analysis methods from the concentration-time data for all subjects in the PK set. Actual sampling times, rather than scheduled sampling times, will be used in all computations involving sampling times. The following PK parameters will be determined from concentrations of CVN424 in plasma:

Symbol/Term	Definition
AUC_{∞}	Area under the plasma concentration-time curve from time 0 to infinity, calculated as $AUC_{\infty}=AUC_t+C_{last}/\lambda_z$, where C_{last} is the last quantifiable concentration.
AUC_6	Area under the plasma concentration-time curve from time 0 to 6 hours, calculated using the linear trapezoidal rule.
\mathbf{C}_{max}	Maximum observed concentration.
CL/F	Apparent clearance after extravascular administration, calculated as Dose/AUC $_{\infty}$ after a single dose.
λ_{z}	Terminal elimination rate constant, calculated as the negative of the slope of the log-linear regression of the natural logarithm concentration-time curve during the terminal phase.
$t_{1/2z}$	Terminal elimination half-life, calculated as $ln(2)/\lambda_z$.
t_{max}	Time to reach C_{max} .
V _z /F	Apparent volume of distribution during the terminal phase after extravascular administration, calculated as (CL/F)/ λ_z .

Additional plasma PK parameters may be calculated, including analyses by gender (if possible). Descriptive statistics (arithmetic mean, SD, median, minimum and maximum) will be used to summarize most plasma (PK) parameters for CVN424. Geometric mean and coefficient of variation will be computed for right-skewed measures, e.g., C_{max} and AUCs. Plots of C_{max} and AUCs versus doses will be generated.

Pharmacodynamic analyses will investigate the possible relationship between CVN424 PK parameters and efficacy and safety outcomes. Population analysis of results may be considered. Details of planned PK analyses will be presented in the SAP.

Study No. CVN424-201 Page 59 of 73

Protocol v. 4.0 14 July 2021

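### Dose dates and times are required only for observed doses, so the last home dose before the Day 8 and 22 troughs and the Day 15, 27 and 35 samples is not captured; this avoidably weakens, but does not prevent, the PK and exposure-response analyses

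*Combined protocol and SAP*

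**What the plan says.** Section 9.2 sets the recording rule: "The date and time of each observed dose will be recorded in the source documents and on the eCRFs". Section 6.1 says which doses are observed: "Dosing on Day 1, Day 8 and Day 22 visits will be observed at the study site by Investigator or their delegate". For the rest, section 9.2 says "Subsequent doses will be self-administered at home, or at the investigative site on selected Study Visit days", and section 6.1 says "Study drug will be self-administered each morning on an outpatient basis as an oral suspension", without a clock time. Home compliance is assessed from bottles returned at weekly visits (sections 8.5 and 9.2).

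Table 5 (section 9.1.13.1) lists these PK samples:
- Days 1 and 8: pre-dose and 3 h after an observed dose.
- Day 22: "Pre-dose and at 1, 1.5, 2, 4, and 6 h post-dose", around an observed dose.
- Days 15 and 27: "Post-dose (time not specified". For Day 27, section 9.3.1.7 adds "An untimed blood sample for PK analysis will be collected".
- Day 35: a washout sample, also without a specified time.

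The actual time of each sample is recorded. On Days 8 and 22 the home dose is withheld until the trough has been drawn.

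Day 22 Cmin is a named parameter in the synopsis. Section 12.1.3 goes further: "Pharmacodynamic analyses will investigate the possible relationship between CVN424 PK parameters and efficacy and safety outcomes". It adds that a population analysis may be considered and leaves PK detail to the SAP.

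The last dosing day is given as Day 27 ±1 (synopsis, section 9.3.1.3), Day 27 or 28 (section 6.1) and Day 28 (section 6.2; Appendix A, note g).

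**The concern.** A recorded sample time can be interpreted only against the time of the preceding dose. For the two troughs and the Day 15, 27 and 35 samples, that dose was taken at home, and the protocol does not ask for its date or time. The Day 27 sample coincides with the main efficacy visit.

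A bottle count may show that a dose was missed that week, but not on which day. A low Day 22 trough could then mean low exposure or a missed Day 21 dose. Section 12.1.1 provides for case-by-case decisions, before unblinding, on subjects who did not keep to the dosing schedule, yet the protocol collects no dated home doses to inform them. Error of this kind in the exposure measure tends to flatten an exposure-response slope.

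**Working it through.** **Inputs.** Terminal half-life 33 h and expected 50 mg trough about 150 ng/mL (section 6.2). Median tmax 1.5 h, fasted (section 4.1). Dosing interval 24 h. Assumed: one compartment, steady state, 2-6 h timing errors, and a 1-8 h window for the Day 15 and 27 samples.

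**The plan's own figure.** Day 28 to Day 35 is 7 × 24 / 33 = 5.09 half-lives, which reproduces the stated figure of about 5.

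**Constants.** k = ln 2 / 33 = 0.0210 per h. Fraction remaining after 24 h: r = 2^(−24/33) = 0.604. At steady state the latest dose supplies 1 − r = 0.396 of the trough. Solving ln(ka/k)/(ka − k) = 1.5 gives ka = 3.42 per h.

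**1. Trough, clock-time error only.**
- Whole schedule shifted by e hours: relative error 2^(e/33) − 1. This is 4.3% at 2 h and 13.4% at 6 h; shifts the other way give −4.1% and −11.8%.
- Only the last dose shifted: 0.396 × (2^(e/33) − 1). This is 1.7% at 2 h and 5.3% at 6 h.

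**2. Day 15 and 27 samples, clock-time error only.** C(t) is proportional to e^(−kt)/(1 − e^(−24k)) − e^(−ka·t)/(1 − e^(−24ka)). Relative to trough, the model gives 1.600 at 1.5 h, 1.459 at 6 h and 1.399 at 8 h, with a peak of 1.603. Over 1-8 h, highest/lowest = 1.603/1.399 = 1.15. Slower absorption (ka 0.8 per h) gives 1.13.

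**3. One undated missed dose.**
- Dose missed the day before: the trough becomes r = 0.604 of usual, so 150 × 0.604 = 91 ng/mL.
- Dose missed two days before: 1 − 0.396 × 0.604 = 0.761 of usual.
- Carry-over into the Day 22 profile: 1.5 h after the Day 22 dose, a Day 21 dose would have contributed 0.396 × 2^(−1.5/33) = 0.384 trough units to a value of 1.600. Its absence costs 0.384/1.600 = 24%. With ka from 0.8 to 3.4 per h, Cmax falls by about 24% and AUC6 by about 24-26%.

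**4. Final dose date.** One day's uncertainty before Day 35 is a factor of 2^(24/33) = 1.66.

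**Sensitivity.** If the effective half-life over the dosing interval were 12-20 h (assumed), a whole-schedule shift of 3 h would give 11-19% and of 6 h 23-41%. The trough after a dose missed the day before would be 2^(−24/20) = 0.44 to 2^(−24/12) = 0.25 of usual.

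**The case against.** The strongest reply is that the planned analysis uses PK parameters, and that Day 22 Cmax, tmax and AUC6 come from timed samples after an observed, timed dose. Only a population model would lean heavily on the untimed samples, and that model is optional. This largely stands. A reader might infer that the missing dose times leave the exposure-response analysis without support; the documents do not bear that out. The limit on the reply is carry-over: observing the Day 22 dose does not show whether the Day 21 dose was taken.

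A reader might also infer that the troughs have no known time since dose. Morning dosing, the withheld dose and the recorded sample time place a compliant trough near 24 h.

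A third tempting reading applies the peak-to-trough ratio, about 1.5 to 1.6, to the Day 15 and 27 samples. Table 5 makes them post-dose, so that ratio is an outer limit, reached only if a near-trough sample is treated as a post-dose one.

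Nor is a missed dose always indistinguishable from low exposure. The bottle count may reveal it, undated, and a subject with persistently low exposure should also be low at the other visits. That comparison is imperfect: in the high-dose arm the Day 8 trough precedes the step to 150 mg, and the Day 15 and 27 samples have no recorded time since dose.

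Finally, the eCRF or SAP may already collect last-dose times. Section 9.2 does not forbid it, and neither was available. That lowers confidence, but section 9.2 remains the instruction to sites, and an analysis plan cannot recover data that were never collected.

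**Conclusion.** The gap is real and limited. The protocol requires date and time only for observed doses, so the last home dose before five sets of PK samples is undocumented. This avoidably weakens the PK and exposure-response analyses in section 12.1.3; it does not prevent them.

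Clock-time error is modest. The larger effects come from an undated missed dose just before Day 8 or Day 22, and from the unsettled final-dose date before Day 35. The sizes rest on the 33 h half-life and, for the profile figures, on a one-compartment steady-state model; a shorter effective half-life would enlarge the trough effects.

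Severity is minor to moderate. Multiple-dose PK is a secondary objective, but the PK parameters are listed as additional and exploratory endpoints, and the primary safety endpoint and the OFF-time endpoint are unaffected. Confidence is moderate, because no separate SAP text or eCRF was available.

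**What to change.** - **Section 9.2:** keep the rule for observed doses. Add that the subject-reported date and clock time of the last two home doses before each PK sample are recorded on the eCRF, for Days 8, 15, 22 and 27, and likewise for the final dose before Day 35 or Early Termination. Two doses are asked for because a miss two days earlier still lowers a trough by about a quarter.
- **Section 12.1.3:** analyse the Day 15, 27 and 35 concentrations by actual time since last dose. Flag Day 8 and Day 22 values, including Day 22 Cmax and AUC6, where the preceding dose was missed.
- **Last dosing day:** reconcile the synopsis, sections 6.1, 6.2 and 9.3.1.3, and Appendix A note g.

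The cost is a date and time entry for each of two doses, and one question to the subject, at each PK visit, with no extra blood or visits. The downside is that home dose times are self-reported.
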